## Overall Response Rate

ORR as assessed by the BIRC, per RECIST 1.1, will be estimated and CIs will be provided per all methods described in [Section 2.7.2](#).

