8.6 Data Monitoring Committee (DMC)

An independent Data Monitoring Committee (DMC) will be constituted and will be responsible for monitoring and reviewing the clinical study data for efficacy and safety during the study prior to the final data analysis. Efficacy data will be reviewed periodically during Stage 1 to advise on whether the trial should proceed to Stage 2 and full enrolment. DMC review for the purpose of advising on the transition of the trial from Stage 1 to Stage 2 will be based primarily on local investigator assessment of response. However, the DMC may request data on assessment of response by the BIRC if deemed necessary. Responsibilities of the DMC, communication flow between DMC, Steering Committee and Novartis, and timing of data safety and efficacy reviews, will be included in the DMC charter document.

It is envisioned that the DMC may make four types of recommendations, namely:

[figure not shown]
[figure not shown]
1. Transition into Stage 2 of the trial or stopping enrollment after stage 1 for futility
2. No safety or ethical issues, ethical to continue the trial as planned
3. Serious safety concerns precluding further study treatment, regardless of efficacy
4. Ethical to continue the study but recommend an amendment to the protocol (e.g. incorporate a safety analysis).

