10.4.4 Supportive analyses

The primary analysis on the FAS will be repeated on the PPS.

ORR, per RECIST 1.1, as assessed by the BIRC, will also be estimated and CIs will be provided based on the FAS as described in [Section 10.4.2](#).

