10.8 Sample size calculation

Based on [Simon's \(1989\)](#) optimal two-stage design, if the true ORR is 50% (under the alternative hypothesis), approximately 105 total patients are required to reject the null hypothesis of $ORR \leq 35\%$ with a one-sided alpha of 0.05 and 90% power. If at least 17 confirmed responses are observed among 43 patients enrolled into Stage 1, an additional 62 patients will be enrolled into Stage 2. If 45 or more confirmed responses are observed among 105 total patients, the trial will be declared positive.

The operating characteristics of the design are described in [Table 10-1](#).

Table 10-1 Operating characteristics of Simon's optimal two-stage design

	True ORR			
	35% (null hypothesis)	40%	45%	50% (alternative hypothesis)
Probability stop for futility at Stage 1 (16 or fewer responses out of 43 patients enrolled at Stage 1)	0.683	0.418	0.192	0.063
Probability trial is success (45 or more responses out of 105 total patients)	0.049	0.268	0.642	0.900

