### **2.7.2 Statistical hypothesis model and method of analysis**

The primary efficacy analysis will be performed on the FAS.

The study targets an ORR of 50%. A response rate of 35% or less is considered as insufficient level of activity for the proposed patient population. Therefore,

$H_0: \text{ORR} \leq 35\%$  will be tested vs  $H_1: \text{ORR} > 50\%$

using a one-sided test with  $\alpha=0.05$  based on Simon's optimal two-stage design ([Simon 1989](#)). If 45 or more responses are seen in 105 total patients (estimated ORR of 42.9%), then  $H_0$  will be rejected and the trial declared positive.

Stage 1 will enroll 43 patients. If the study is terminated early at the end of Stage 1 (16 or fewer responses among 43 patients enrolled to Stage 1), then the study will be considered to have failed to reject  $H_0$ . See [Section 2.11](#) for further details of the stopping criteria for futility. Stage 2 will include an additional 62 patients. The primary analysis will occur when all 105 patients have completed 6 cycles of treatment or discontinued treatment earlier.

The ORR will be estimated and the 90% and 95% Clopper-Pearson (Clopper and Pearson 1934) confidence intervals (CIs) will be provided. The uniformly minimum variance unbiased estimator (UMVUE) and the 90% two-stage CI (Atkinson and Brown 1985) will also be presented. Refer to Section 4.6.4 for additional details.

Clopper-Pearson confidence intervals will be used since the confidence limits based on the normal approximation are not bounded by the  $[0, 1]$  interval, meaning that for rates close to 0 or 1, the upper limit of the normal approximation interval for the proportion could exceed 1 or the lower limit could be negative. The 90% two-stage CI will be presented to correspond to the Simon two-stage p-value.

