Primary Objective; Section 10.5.1 - Key Secondary Objective(s)	the calculation of 90% CIs given that the primary endpoint is tested at one-sided 5% significance level	primary endpoint will show the 90% CI as per protocol as well as 95% naive CIs. For other secondary endpoints only 95% CIs will be displayed	that across the LDK378 program, all efficacy endpoints are summarized using 95% CIs

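### BIRC ORR is also given the UMVUE and Atkinson-Brown interval, which assume a Stage 1 gate on BIRC responses that the plan does not contain

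*SAP*

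**What the plan says.** For BIRC ORR, SAP 2.8.1 (Overall Response Rate) states that it "will be estimated and CIs will be provided per all methods described in" SAP 2.7.2. That section gives the observed ORR with 90% and 95% Clopper-Pearson intervals and then adds: "The uniformly minimum variance unbiased estimator (UMVUE) and the 90% two-stage CI (Atkinson and Brown 1985) will also be presented". Its stated reason for the two-stage interval is agreement with the Simon two-stage p-value.

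The instruction starts in the protocol. Under Protocol 10.4.4, ORR "as assessed by the BIRC, will also be estimated and CIs will be provided based on the FAS as described in" Protocol 10.4.2, which also contains the UMVUE and the two-stage interval.

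Protocol 10.7 and SAP 2.11 base the Stage 1 decision (stop at 16 or fewer responses in 43 patients) on local investigator assessment. Protocol 8.6 says that the review "will be based primarily on local investigator assessment of response". All three sections let the DMC ask for BIRC data. None sets a BIRC bound.

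Three places bear on the interval level. The protocol synopsis (Data analysis) gives a 90% CI for ORR by investigator and by BIRC. SAP 4.6.4 gives 90% and 95% intervals for ORR without limiting this to investigator ORR. SAP Table 3-1, in a row that covers the key secondary objectives, says: "For other secondary endpoints only 95% CIs will be displayed".

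**The concern.** The UMVUE and the Atkinson-Brown interval correct for selection: a trial reaches Stage 2 only when its own Stage 1 count was at least 17. Applied to BIRC counts, they treat a continuing trial with 16 or fewer BIRC responses at Stage 1 as impossible. Under an investigator gate it is possible, so the estimator loses its unbiasedness and the interval does not describe how the BIRC count varies.

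BIRC ORR is a key secondary endpoint and an independent reading of an investigator-assessed primary endpoint in an open-label, single-arm trial. The unwarranted correction is largest when the BIRC result is low. It would then narrow the gap between the two assessments in exactly the case where that gap is of interest. The UMVUE is also labelled unbiased and would stand beside the plain proportion with no note that its assumption fails.

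**Working it through.** **Inputs.** Stage 1: 43 patients, stop at 16 or fewer. Stage 2: 62 more. Success: 45 or more of 105 (SAP 2.7.2). Null rate: "A response rate of 35% or less is considered as insufficient level of activity for the proposed patient population". Target: "The study targets an ORR of 50"%. Error rates: "with a one-sided alpha of 0.05 and 90% power" (Protocol 10.8). Phase I ORR in crizotinib-naïve patients: 60% at 400 mg or above (Protocol 1.2.1.2.2). The true BIRC ORR and the correlation φ between the two assessments are not in the documents. They are assumptions, shown as ranges.

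**Step 1: reproduce the design.** With b the binomial probability,

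P(stop) = P(Bin(43, p) ≤ 16)

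P(success) = Σ(x = 17 to 43) b(x; 43, p) · P(Bin(62, p) ≥ 45 − x)

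| True ORR | 35% | 40% | 45% | 50% |
|---|---|---|---|---|
| P(stop) | 0.6828 | 0.4178 | 0.1916 | 0.0631 |
| P(success) | 0.0487 | 0.2678 | 0.6418 | 0.9000 |

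These match SAP Table 2-3.

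**Step 2: where the gate enters.** For s responders in 105,

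UMVUE(s) = Σ(x ≥ 17) C(42, x−1)·C(62, s−x) ÷ Σ(x ≥ 17) C(43, x)·C(62, s−x)

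If x ran over all values, this would be C(104, s−1) ÷ C(105, s) = s/105. The whole difference from the observed proportion therefore comes from excluding Stage 1 counts of 16 or fewer. At s = 45 the expected Stage 1 share is 43 × 45/105 = 18.4, close to the bound. At s = 63 it is 25.8, and the exclusion hardly matters.

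The Atkinson-Brown 90% limits solve the two-stage tail probabilities at 5% per side, with futility stops ranked lowest.

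**Step 3: size of the shift (90% intervals, 105 patients).**

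| BIRC responders | Observed (Clopper-Pearson) | UMVUE (Atkinson-Brown) | Shift in estimate |
|---|---|---|---|
| 40 | 38.1% (30.2–46.6) | 42.9% (31.4–51.0) | +4.8 |
| 45 | 42.9% (34.7–51.4) | 45.1% (35.1–52.6) | +2.2 |
| 50 | 47.6% (39.3–56.1) | 48.3% (39.3–56.3) | +0.7 |
| 53 | 50.5% (42.0–58.9) | 50.8% (42.1–58.9) | +0.3 |
| 63 | 60.0% (51.5–68.1) | 60.0% (51.5–68.1) | 0 |

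At low counts both limits rise, the upper more than the lower (40 responders: +4.5 and +1.2 points).

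The protocol's amendment rationale reports 124 treated patients, and the SAP does not say which Stage 2 size the formulas take. With 124 − 43 = 81, the shift is +2.5 points at 53/124 (42.7%), +0.3 at 63/124 (50.8%) and 0 at 74/124 (59.7%).

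**Step 4: how much of the shift is bias.** Give each patient a correlated pair of responses, let the trial continue if the investigator count is at least 17, and apply both estimators to the BIRC responses. Bias is in points, unconditional.

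| Investigator / BIRC rate | φ | UMVUE | Observed proportion | BIRC Stage 1 count ≤ 16 in a continuing trial |
|---|---|---|---|---|
| 60% / 50% | 0 to 0.7 | +0.7 | about 0 | 6% |
| 60% / 45% | 0 to 0.7 | +1.9 | about 0 | 19% |
| 60% / 40% | 0 to 0.65 | +4.1 | about 0 | 42% |
| 50% / 45% | 0.72 | +1.3 | −0.4 | 15% |
| 50% / 40% | 0.65 | +3.3 | −0.4 | 38% |
| 50% / 50% | 0.8 | +0.1 | −0.5 | 3% |
| 45% / 45% | 0.8 | +0.3 | −1.0 | 8% |

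At an investigator rate of 60%, 99.8% of trials continue. There is then almost no selection to correct, and the correlation barely matters.

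**The case against.** A reader might infer that the reported BIRC ORR itself is inflated. It is not: SAP 2.7.2 puts the ordinary proportion and its Clopper-Pearson intervals first, and BIRC ORR receives these too. Only two supplementary figures move. This stands.

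A reader might also treat the whole shift as error. The last two rows of Step 4 contradict that. With equal true rates and high agreement, the investigator gate also selects on BIRC responses, and the UMVUE is closer to unbiased than the plain proportion. Conditional on continuing it sits higher, but so does the investigator UMVUE. This stands as well.

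The larger biases need an investigator-BIRC gap of 15 to 20 points, for which the documents give no evidence. At 60% against 55% the bias is under 0.2 points. Equally, the documents do not exclude such a gap, and a large disagreement is what an independent review is there to show.

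BIRC ORR is not the only independent check: DCR, DOR, TTR and PFS are also analysed by BIRC. Nor do the documents show that the DMC saw no BIRC data. They describe a plan based primarily on investigator responses, with BIRC data on request. Even so, the two-stage formulas need a BIRC bound of 17, and none is written.

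Finally, there is no hypothesis or success rule for BIRC ORR, and multiplicity is not adjusted. That limits the importance of the point but supplies no reason for using the methods.

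**Conclusion.** The point holds for the two supplementary figures only. The UMVUE and the Atkinson-Brown interval rest on a Stage 1 condition that the plan places on investigator responses, so for BIRC ORR they lack the properties their names imply. Every shift found was upward or nil. At an observed BIRC ORR of roughly 38% to 48% the estimate moves by about 5 down to 0.7 points.

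How much of this is bias depends on two quantities that the documents do not give: the true BIRC rate and its agreement with the investigator. It is material when BIRC ORR is well below investigator ORR, and small when the two agree closely.

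The interval-level wording is a lesser matter. SAP 2.8.1 is specific and Table 3-1 is general, so they can be read together, but a programmer should not have to choose. The trial's success rule and the plain BIRC ORR are unaffected, and the priority is low.

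**What to change.** In SAP 2.8.1 (Overall Response Rate), replace the reference to every method of 2.7.2 with wording such as:

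> ORR by BIRC will be reported as the observed proportion with exact Clopper-Pearson 90% and 95% CIs. The UMVUE and the two-stage CI will be given for investigator-assessed ORR only, because the Stage 1 rule is defined on investigator-assessed responses.

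If the two-stage figures are kept for BIRC, footnote them as assuming a Stage 1 gate on BIRC responses.

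Record this in SAP Table 3-1 as a change from Protocol 10.4.4. State there that the line limiting secondary endpoints to 95% intervals does not cover BIRC ORR, for which the protocol synopsis gives a 90% interval.

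The cost is one SAP sentence and an edit to Table 3-1. The downside is that one pre-specified supplementary analysis is dropped or relabelled. The observed BIRC ORR and its exact intervals stay as planned.

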## Best overall response

The BOR will be assessed based on reported lesion responses at different evaluation time points. Both CR and PR require confirmation at least 4 weeks after its initial observation.

Only tumor assessments performed before the start of any further anti-neoplastic therapies (i.e. any additional secondary anti-neoplastic therapy or anti-cancer surgery) will be considered in the assessment of BOR. If a patient receives any further anti-neoplastic therapy while on study, any subsequent assessments will be excluded from the BOR determination. Further anti-neoplastic therapies will be identified via protocol deviations or from the data collected on 'Anti-neoplastic therapies since last date of study drug' as appropriate. Clinical deterioration will not be considered as documented disease progression. Patients with BOR 'unknown' will be summarized by reason for having unknown status. The following reasons will be used:

- No valid post-baseline assessment
- All post-baseline assessments have overall response UNK
- New anti-neoplastic therapy started before first post-baseline assessment
- Stable disease (SD) too early ( $\leq 6$  weeks after start date of study drug)
- PD too late ( $> 12$  weeks after start date of study drug)

Special (and rare) cases where BOR is 'unknown' due to both early SD and late PD will be classified as 'SD too early'.

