7.2.1.2 Subsequent image assessments for response determination

Tumor assessment for response determination will be made every 8 weeks starting from Day 1 of cycle 1 (+/- 7 days window). **The 8 weeks interval should be respected regardless of whether treatment with LDK378 is temporarily withheld.**

Post-baseline tumor assessments

The following assessments will be performed at on-study scheduled visits (see [Table 7-1](#)):

- Computed Tomography (CT) or Magnetic Resonance Imaging (MRI) of chest and upper abdomen.
- Localized CT, MRI or X-rays of all skeletal lesions identified on the screening bone scan, which are not visible on the chest and upper abdomen CT/MRI (and pelvis CT/MRI if applicable). Whole body bone scans need not be repeated after baseline unless clinically indicated.
- Brain CT with IV contrast or MRI, if brain metastases were identified at baseline.
- Color photographs (with a metric ruler) if skin lesions were documented at baseline.
- CT or MRI of any other site of disease documented at baseline (e.g., pelvis, neck).

For post-baseline tumor assessments, all lesions that were present at baseline must be accounted for using the same technique as used at baseline so that the comparison is consistent. If possible, a single radiologist should perform all tumor response evaluations for an individual patient.

All study imaging performed, including any intercurrent imaging studies, whether or not suspected to fulfill a progression or response criterion, should be submitted to the designated imaging CRO for quality control and the BIRC review promptly after acquisition. The activities of the imaging CRO and the BIRC will be described in the Imaging Charter.

Criteria required for determining partial or complete response should be confirmed by a subsequent imaging assessment at least 4 weeks later. If an off-schedule imaging assessment is performed to confirm response or if progression is suspected, subsequent imaging assessments should be performed in accordance with the original imaging schedule unless the next scheduled imaging timepoint is within 2 weeks, in which case the scheduled imaging timepoint can be omitted.

Combined PET/CT may be used only if the CT is of similar diagnostic quality as a CT performed without PET, including the utilization of oral and IV contrast media. At the discretion of the Investigators, FDG-PET scans may be performed to document progressive disease per RECIST 1.1 ([Appendix II](#)).

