### 2.7.3 Handling of missing values/censoring/discontinuations

Confirmed PR or CR reported prior to any additional anticancer therapy will be considered as responses in the calculation of the ORR in respect of the number of missed assessments before response.

Patients with a best overall response (BOR) of 'Unknown' or 'Not Assessed per RECIST 1.1' will be considered as non-responders when estimating ORR.

Patients who have disease progression and continue to receive study drug after progression will qualify for PD at the time of progression and will be counted as PD in the derivation of ORR and any other efficacy endpoints.

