### **Determination of missing adequate tumor assessments**

For the computation of ORR, patients without any radiological assessment after the start date of study drug will be counted as failure.

Partial or complete responses reported prior to any additional anticancer therapy will be considered for ORR computation in respect of the number of missed assessments before response. In this section, the 'missing adequate assessment' is defined as assessment not done or assessment with overall lesion response equal to UNK. For the sake of simplicity, the 'missing adequate assessment' will also be referred as 'missing assessment'.

As detailed in Section 14 (Appendix II) of the LDK378A2203 protocol, the PFS censoring and event date options depend on the presence and the number of missing tumor assessments. *For example, an event occurring after two or more missing assessments is censored at the analysis of PFS at the last adequate tumor assessment before the event date.*

An exact rule to determine whether there is none, one or two missing assessments is therefore needed. This rule will be based on the distance between the last adequate tumor assessment date and the event date.

If the distance is larger than threshold D1 or D2 then the analysis will assume one or two missing assessments, respectively. The threshold D1 will be defined as the protocol specified interval between the tumor assessments plus the protocol allowed window around the assessments. Similarly, the threshold D2 is defined as two times the protocol specified interval between the tumor assessments plus the protocol allowed window around the assessments. In this study, the protocol defined schedule of tumor assessment is every 8 weeks and each assessment is expected to be performed at the scheduled time point plus or minus 1 week, i.e. the window is 2 weeks, then any distance larger than  $D1 = 8 + 2 = 10$  weeks means one missing assessment and any distance larger than  $D2 = (2 * 8) + 2 = 18$  weeks means two missing assessments.

The same definition of D2 will be used to determine the PFS censoring reason. If the distance between the last adequate tumor assessment date and one of the following dates is  $\leq$  D2:

1. Analysis cut-off date
2. Start date of farther anti-neoplastic therapy
3. Visit date of study treatment discontinuation due to consent withdrawal
4. Visit date of study treatment discontinuation due to loss to follow-up

then the associated censoring reason will be

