### **Non-measurable disease at baseline**

As specified in Section 14 (Appendix II) of the LDK378A2203 protocol, the RECIST 1.1 criteria imply that only patients with measurable disease at baseline should be included in the study. If a patient without measurable disease is enrolled, the intent-to-treat (ITT) principle requires including these patients in the analyses. Hence, analyses will be based on FAS including patients with either measurable or non-measurable disease. Therefore, a rule needs to be specified on how to handle these cases.

As specified in Table 3-1 of Section 14 (Appendix II) of the LDK378A2203 protocol, overall lesion response can be derived for patients without measurable disease at baseline.

Target lesion response will always be UNK due to missing baseline measurements. Therefore, a CR, PR or SD can never be assigned as an overall lesion response. However, a PD can still be determined from non-target lesions or from new lesions.

As a result, the overall lesion responses will always be UNK until PD occurs. The BOR will either be UNK or PD depending on the timing of PD (if PD is observed  $>$  17 weeks, it will be considered as UNK). The PFS censoring and event date options will depend on how many UNKs precede the PD.

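### Two SAP limits for a progression too late to be best response: 12 and 17 weeks conflict for non-measurable disease, and the 12-week limit shuts out the on-time second scan

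*SAP*

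**What the plan says.** SAP 2.8.1, under *Best overall response*, lists the reasons to be tabulated when BOR is Unknown. Two depend on time since first dose: "Stable disease (SD) too early ( $\leq 6$ weeks after start date of study drug" and "PD too late ( $> 12$ weeks after start date of study drug". Neither is restricted to a type of patient. A patient who has both an early SD and a late PD is assigned to the early-SD reason.

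SAP 4.6.1, under *Non-measurable disease at baseline*, covers patients enrolled without measurable disease. It states: "As a result, the overall lesion responses will always be UNK until PD occurs". BOR is then either PD or UNK according to when the PD is seen: "if PD is observed $>$ 17 weeks, it will be considered as UNK".

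The scan schedule is the same in both documents. Protocol 7.2.1.2 has "Tumor assessment for response determination will be made every 8 weeks starting from Day 1 of cycle 1 (+/- 7 days window", and SAP 4.6.1 repeats that "the protocol defined schedule of tumor assessment is every 8 weeks".

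The table of changes in SAP section 3 mentions neither limit. The SAP gives no reason why they differ.

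**The concern.** A patient with non-measurable disease is subject to both rules. If PD is first seen after week 12 and by week 17, one section makes BOR Unknown and the other makes it PD, so a programmer cannot follow both.

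The 12-week limit also fits no scheduled scan, because it falls between the first and the second. A patient whose week-8 scan was missed or UNK, and who then has documented PD at an on-time week-16 scan, is tabulated as Unknown. What is at stake is the descriptive BOR table, by investigator and by BIRC. Documented early progression would move from the PD row to the Unknown row, and the split would depend on which section the programmer followed.

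**Working it through.** **Inputs.** Scan interval 8 weeks, window plus or minus 1 week (Protocol 7.2.1.2; SAP 4.6.1). Limits of 12 weeks (SAP 2.8.1) and 17 weeks (SAP 4.6.1). SD qualifies after 6 weeks (SAP 2.8.1). 124 patients treated (Protocol, Amendment 4 rationale).

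**1. The SAP's own schedule figures.** SAP 4.6.1 derives its missing-scan thresholds as D1 = 8 + 2 = 10 weeks and D2 = 2 x 8 + 2 = 18 weeks. Both reproduce.

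**2. Scan windows from first dose**, k x 8 plus or minus 1 week:

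| Scan | Window (weeks) | Beyond 12? | Beyond 17? |
|---|---|---|---|
| 1 | 7 to 9 | none of it | none of it |
| 2 | 15 to 17 | all of it | none of it |
| 3 | 23 to 25 | all of it | all of it |

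The 17-week limit equals 2 x 8 + 1, the end of the second window. It carries one week of window rather than D2's two because it runs from a fixed date, not between two scans. That is an inference; the SAP does not explain the figure.

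**3. BOR when PD is first seen at weeks 15 to 17:**

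| Before that PD | 12-week limit | 17-week limit |
|---|---|---|
| SD at an on-time first scan (weeks 7 to 9) | SD | SD |
| Week-8 scan missed or UNK | Unknown (PD too late) | PD |
| SD only at 6 weeks or earlier | Unknown (SD too early) | PD |
| Non-measurable disease (UNK until PD) | Unknown (PD too late) | PD |

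In the last row both limits are written into the SAP for the same patient. In the second and third rows, if disease is measurable, only the 12-week limit is stated.

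**4. PFS for the same progression.** SAP 4.6.1 counts a UNK scan as missing. SAP Table 2-1, row C1, treats PD after exactly one missing assessment as an event on the date of progression. Counted from first dose, weeks 15 to 17 lie between D1 = 10 and D2 = 18, so exactly one scan is missing. One caveat applies: the threshold runs from the last adequate assessment. If that is a baseline scan more than 18 - 15 = 3 weeks (PD at week 15) or 18 - 17 = 1 week (PD at week 17) before first dose, the distance exceeds 18 weeks and row C2 would censor. The SAP does not say whether the count then starts at the scan or at first dose. This is a PFS matter and does not depend on which BOR limit is used.

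**5. Effect on endpoints.** Patients with Unknown BOR "will be considered as non-responders when estimating ORR" (SAP 2.7.3), and PD is a non-response too. Neither category is in the DCR numerator (SAP 2.8.1). PFS has its own rules. Change in ORR, DCR and PFS: 0.

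**6. Size in the BOR table.** The documents give no rates, so these are assumptions: 5% to 15% of patients have no evaluable week-8 response, and PFS is exponential with a median of 18 to 8 months, independent of evaluability. With M = median x 30.4375 / 7 weeks and S(t) = 0.5^(t/M):

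- Median 18 months: M = 78.3, S(8) = 0.932, S(16) = 0.868. PD between weeks 8 and 16: 0.064. PD by week 16: 0.132.
- Median 8 months: M = 34.8, S(8) = 0.853, S(16) = 0.727. PD between weeks 8 and 16: 0.126. PD by week 16: 0.273.

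Counting only PD arising between weeks 8 and 16: 124 x 0.05 x 0.064 = 0.4 to 124 x 0.15 x 0.126 = 2.3 patients per reader. If the week-8 scan was missed altogether, PD arising before week 8 is also first seen at week 16: 124 x 0.05 x 0.132 = 0.8 to 124 x 0.15 x 0.273 = 5.1. Each patient is 1/124 = 0.8 percentage points.

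**The case against.** The 17-week sentence is written only for patients without measurable disease, and such patients are ineligible (Protocol 5.2, criterion 10, and 7.2.1.1). For a patient with measurable disease and a missed week-8 scan, SAP 2.8.1 is the only rule shown, so there is no textual contradiction there. The SAP also defers to the RECIST guideline in protocol Appendix II for response evaluation. The detail of that appendix is not in the text available here, and it could support either number. No endpoint moves, Unknowns are printed with their reason, and the rate of PD as best response is not a listed endpoint. The DCR definition also admits a BOR of Non-CR/Non-PD, which might take some non-measurable patients out of the Unknown group altogether.

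Nearly all of this stands, and it sets the scope and the severity. Two things survive. First, the SAP itself plans for enrolled patients without measurable disease, and a BIRC reader may find no target lesion where the investigator did. The direct conflict therefore concerns patients the SAP expects to handle. Second, whatever Appendix II says, a 12-week limit under an 8-week schedule leaves no on-time second scan at which a first PD could count, and the SAP does not say that this is intended.

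**Conclusion.** This is a minor internal inconsistency. For non-measurable disease the two sections conflict for PD seen after week 12 and up to week 17. For any patient with no earlier qualifying response, the 12-week rule reports PD at an on-time second scan as Unknown, while row C1 of the PFS table counts PD after one missing or UNK scan as an event. Under the assumed rates this moves between under one and about five patients per reader between the PD and Unknown rows.

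Three stronger readings are tempting, and the documents support none of them:

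- That every PD at the second scan becomes Unknown. SD at an on-time first scan is later than 6 weeks and gives BOR = SD under either limit.
- That the primary result or another efficacy endpoint is at risk. ORR, DCR and PFS are unchanged.
- That 17 weeks is shown to be the intended rule. It fits the schedule, but Appendix II cannot be checked here.

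**What to change.** State one limit and use it in SAP 2.8.1 (including the tabulated reason) and in 4.6.1, for investigator and BIRC alike. Tie it to the scan schedule: more than 17 weeks, given as two 8-week intervals plus the 1-week window. Before changing the text, check the BOR rule in protocol Appendix II and the rule used for the primary CSR. If the primary CSR used 12 weeks, add a line to the SAP's table of changes and a footnote to the BOR table, so that the PD and Unknown rows of the two reports can be compared. If 12 weeks is kept on purpose, say why and bring 4.6.1 into line.

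The cost is one number in the SAP, one constant in the BOR program, and the check against the two sources.
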